Arrest of caries lesions will be determined by assessing clinical hardness, colour change, and size of lesions at baseline, at second visit, and at the final study visit. Children will be recruited and we will perform block randomization by site in order to achieve equal proportions in each regimen by clinic site of recruitment. Study visits will occur at the Children's Hospital Research Institute of Manitoba (CHRIM) or at community-based dental clinics. Following informed consent the child's parent/caregiver will complete a short questionnaire (via interview) on general and dental health, oral hygiene, dietary intake of sugars, and family demographics along with the ECOHIS to assess OHRQL. SDF will be applied on the day of recruitment to cavitated lesions involving dentin followed by 5% NaFV. Depending on which frequency regimen children are randomized to, they will return for a second visit. During this second visit, caries lesions treated with SDF at baseline will be assessed to see if caries is arrested as determined through measures of hardness, colour change, and size. At this same visit a second application of SDF will be applied to these initially treated caries lesions followed by 5% NaFV. Children and parents will return for the third and final study visit according to the schedule of their randomized grouping. Parents/caregivers will complete a follow-up questionnaire similar to the

baseline tool. Caries lesions previously treated by SDF will be assessed for clinical hardness, colour change and size to determine if they have arrested.

Population: As ECC is age specific, participants will be < 72 months of age with active caries and their parents/caregivers. The majority will be recruited from community-based dental clinics in Winnipeg (i.e., Access Downtown, Mount Carmel Clinic, and SMILE Plus Children's Dental Clinic) or who are currently on a wait list for dental surgery under general anesthesia in Winnipeg. We found that these were ideal sites for our recently completed feasibility trial of SDF. We will restrict participation to children living in the Winnipeg region or within a one hour drive of Winnipeg to minimize the risk of loss-to-follow-up. Eligibility criteria are designed to select young children who have active caries, and thus are at an increased risk of morbidity from existing caries and onset of new caries.

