Inclusion Criteria: 1) Child is < 72 months of age with ECC with active caries lesions; 2) Child has ≥ 1 primary tooth with caries that is eligible to receive SDF. Eligible primary teeth must: a) have soft cavitated caries lesions extending into dentin (ICDAS 5 or 6); b) the cavitated lesions must allow for direct application of SDF. Teeth that meet any of the PUFA criteria (i.e. spontaneous pain due to caries, pulp exposure, mobility, signs of pulpal infection such as abscess, fistula, or swelling) will be excluded. However, a child would still be eligible even if they have at least one tooth that meets PUFA criteria, but other eligible teeth with caries do not.

Exclusion Criteria: 1) Child is allergic or has sensitivity to silver or other heavy metal ions; 2) Child has hereditary generalized developmental defects of enamel (e.g., amelogenesis imperfecta, dentinogenesis imperfecta); 3) Child has severe medical problems that limit participation; 4) Child requires immediate rehabilitation under general anesthesia because of severe infection or pain; 5) Antibiotic use within the last 2 weeks (for the microbiome sub-study).

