Sample and Justification of Sample Size: Sample size for this pilot study has been determined in discussion with [name] (collaborator, Professor & Biostatistician). Our intent is to compare arrest rates between groups and to see whether the three different regimens will yield arrest rates within a range of what we will determine to be clinically acceptable. Based on our recent pilot feasibility study of SDF with 40 children (with 239 lesions) we reported an arrest rate of approximately 96% following two applications of SDF. Results from a recent systematic review state that 80% of lesions can arrest because of SDF. We believe that a range of arrest rates from 80% to 96% yield similar beneficial outcomes in the clinical setting. Based on our pilot study, 40 children had 239 lesions (average 6 lesions/child). With our pilot sample of 239 lesions, it is possible to estimate an arrest rate with a 95% confidence interval to be accurate within $\pm 6.5\%$. With 400 lesions anticipated in our proposed recruitment sample, the 95% confidence interval for the arrest rate would be $\pm 5.0\%$. We propose three SDF regimen groups and anticipate that each group will have 22 children anticipating an average of six lesions. This would mean 396 lesions would be followed in this study. We anticipate that with 400 lesions the percent of arrest will be within $\pm 5\%$ if we have 22 children in each group. To deal with potential drop-outs and loss-to-follow-up of up to 20% we will over recruit by into each group and recruit 28 per group. We anticipate that we can successfully recruit 10 children each month.

Instrumentation and Outcome Measures: Baseline and follow-up visit questionnaires will be a modified versions of those used in our SDF pilot feasibility study (developed by [name] [collaborator] in her SDF efficacy study). The questionnaire collects child and family

demographic information, oral hygiene and use of toothpaste, dietary habits (i.e., snack foods and drinks), consumption of fluoridated water, appearance of the teeth, and symptoms (e.g., pain). The tools also include sections for the parent/caregiver to complete with their child on how the child believes their teeth look and feel and how they rated their visit and SDF treatment.

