The Early Childhood Oral Health Impact Scale (ECOHIS) will be used to assess changes in OHRQL from baseline to completion of study. ECOHIS is a validated tool for use with parents/caregivers of children < 72 months of age. It consists of 13 questions grouped into two sections: 1) child impact, and 2) family impact. The child impact section includes nine questions in four areas: 1) symptoms, 2) functions, 3) psychology, and 4) self-image and social interaction. The family impact component covers two areas: 1) parental distress and 2) family function. Each question is scored from 0 to 5 [0= never, 1= hardly ever, 2= occasionally, 3 = often, 4= very often, 5= don't know]. A total score for each child is calculated by summing up response codes. The ECOHIS will allow us to calculate and compare mean ECOHIS scores at each visit and between groups. Our team has experience with analyzing ECOHIS.

Clinical outcomes assessed will include the proportion of teeth arrested (i.e., "arrest rate" = total number teeth arrested / total number of teeth treated), the proportion of children with any arrested caries, associated morbidity (dental pain and, dental abscess assessed using the PUFA index), and proportion of children requiring dental surgery under GA. The PUFA index is a score of the consequences of severely decayed teeth with visible pulpal involvement (P/p), ulceration caused by dislocated tooth fragments (U/u), fistula (F/f) and abscess (A/a). We will also record dmft and dmfs scores for each child at baseline and at subsequent study visits. The dmft and dmfs scores are cumulative counts of the total number of primary teeth or surfaces decayed, missing due to, or filled because of caries.

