Our research staff will contact interested parents/caregivers and will inform them of the study objectives, eligibility criteria, and procedures. Children will undergo a dental screening by the principle investigator or a calibrated and trained dental examiner to determine whether children meet the clinical criteria for this study by having cavitated caries lesions involving dentin (i.e. ICDAS category 5 or 6). Since ECC is more common in disadvantaged populations, we will arrange for transportation (i.e., taxis) for participants. We also anticipate that some participants will be newcomers and will require interpreters. We will arrange for WRHA interpreters when needed. Visits will occur at the principle investigator's dental suite at CHRIM or at one of the community-based clinics.

Baseline visit: Following written informed consent, children will be randomly allocated into one of three groups using sealed envelopes to ensure random allocation. Parents/caregivers will complete the baseline questionnaire administered by interviewer. Children will undergo a dental examination (without x-rays) to record the number of teeth and tooth surfaces with caries meeting ICDAS 5 or 6 criteria and the specific tooth numbers. We will record the location, size, hardness, colour, and activity status of each eligible caries lesion. We will also assess the total number of primary teeth and tooth surfaces affected by caries (i.e., dmft and dmfs). We will also determine the PUFA index. SDF will then be applied with a microbrush for one minute to each cavitated lesion meeting the eligibility criteria followed by 5% NaFV.

Second visit: Depending on the regimen children will return 4 months (Regimen 1), 6 months (Regimen 2), or 1 month (Regimen 3) later for their first follow-up visit and second application of SDF. Parents/caregivers will complete the ECOHIS tool. Prior to the second application of SDF, caries lesions that received the first application of SDF will be assessed to determine if caries is arresting. Lesions will be assessed for colour change, size, and hardness. Clinical data will be recorded including dmft, dmfs, and PUFA scores will be recorded. Following the dental assessment of the lesions under investigation, SDF will be applied to these lesions for one minute followed by 5% NaFV.

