PowerSoil Kit (Qiagen). It allows the isolation of genomic DNA (gDNA) from fungi and Gram (+-) bacteria, which will be used for downstream analyses. For the 16S rRNA (bacteriome) and ITS1 rRNA (mycobiome) amplicon sequencing, isolated gDNA will be used for PCR amplification of the V4 region of the bacterial 16S rRNA gene, and for PCR amplification of the fungal Internal Transcribe Spacer 1 (ITS1) rRNA gene. gDNA will be sequenced at Génome Québec using paired-end Illumina MiSeq PE250 sequencing. Data analysis will be performed in the [name] lab using established methods. Briefly, demultiplexed raw sequencing results will be filtered and clustered into operational taxonomic units (OTUs) and alpha and beta diversity analyses performed using QIIME2 (Quantitative Insights into Microbial Ecology) v. 2018.11. 16S sequences will be aligned and taxonomy assigned with the HOMD database. ITS1 sequences will be aligned and taxonomy assigned with the UNITE database.

Data Analysis:

This study will estimate the success of different SDF. Descriptive statistics will be used (e.g. frequencies, proportions, and means \pm standard Deviations). The “arrest rate” (primary outcome) will be calculated for the second visit and again at the third and final visit. Bivariate analyses will assess changes in clinical measures and survey data from baseline to the follow-up. McNemar’s test will be used to compare the arrest rate between the second and third clinical visits and to compare dichotomous data from the baseline questionnaire with that from the follow-up questionnaire within each regimen. Chi-squared analysis will compare arrest rates between the regimen groups. Paired t-test will be used to compare normally distributed interval data from the baseline questionnaire with that from the follow-up questionnaire within regimens (Mann-Whitney test if not normally distributed). We will rely on repeated measures analysis of variance to assess changes in ECOHIS scores and other continuous data over time (i.e. baseline vs. second visit vs. final study visit) within each regimen group and to assess differences between regimen groups. Although this is a pilot RCT, we will explore potential changes in the oral microbiome of those randomized to different regimens. This will provide insights into potential mechanisms of SDF action, whether it has antimicrobial activity and influences the oral microbiome composition. A p value ≤ 0.05 will be significant.

Ethics:

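### The primary between-regimen arrest test is an unadjusted chi-squared test that uses neither recorded baseline lesion size nor the clustering of teeth within randomised children; the cost of omitting size is lost precision, not bias

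*Combined protocol and SAP*

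**What the plan says.** The Data Analysis section fixes the primary outcome and its timing: "The “arrest rate” (primary outcome) will be calculated for the second visit and again at the third and final visit". Under Instrumentation and Outcome Measures the rate is defined per tooth, as "total number teeth arrested / total number of teeth treated". The only method given for comparing regimens on it is "Chi-squared analysis will compare arrest rates between the regimen groups". The other arrest analysis, McNemar's test, compares visits two and three. No regression or stratified analysis of arrest appears.

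The Baseline visit paragraph says "We will record the location, size, hardness, colour, and activity status of each eligible caries lesion", and this happens before SDF is applied. Data Analysis gives these measurements no part in the regimen comparison. The only remark about a covariate, under Ethics, is that First Nations status will not be one.

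On balance, the Design section says "we will perform block randomization by site in order to achieve equal proportions in each regimen by clinic site of recruitment". Nothing balances lesion features. On size, the sample-size section expects that "each group will have 22 children anticipating an average of six lesions", and adds "This would mean 396 lesions would be followed in this study".

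**The concern.** Arms of 22 evaluable children are small, and lesions arrive about six to a mouth. If large lesions tend to occur in the same children, 132 lesions per arm balance less well than 132 independent lesions would, and blocking by site does not help. If larger lesions arrest less often, part of any observed regimen difference, or of any apparent similarity, will reflect which lesions each arm happened to receive. A chi-squared test has no place for a covariate, so it cannot remove that part.

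This matters because Hypothesis 1 is that the regimens give similar arrest rates, and the closing section intends the results to inform a larger trial. Avoidable noise makes both a difference and a similarity harder to read. Naming the covariate in advance also prevents an adjustment being chosen after the results are seen.

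**Working it through.** **The plan's own figures.** With lesions treated as independent and p = 0.5, the half-width is 1.96 × √(0.25/n).
- n = 400 gives 4.90% (5.03% with continuity correction), against the stated ±5.0%.
- n = 239 gives 6.34% (6.55% with correction), against ±6.5%.
- 3 × 22 × 6 = 396 lesions, and 22/0.80 = 27.5, rounded up to 28 per group.

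The figures reproduce, but only if clustering within children is ignored.

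**Inputs for the imbalance.** From the documents: 22 children and six lesions per arm (132 lesions), and arrest rates of 96% (pilot) and 80% (systematic review). Assumed: 88% as the midpoint, within-child correlation of lesion size (ICC) 0.2 to 0.4, and odds of arrest falling 1.5-, 2- or 3-fold per SD of size.

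**Step 1: chance imbalance in mean size between two arms, in SD units.** SD = √(2 × (1 + 5 × ICC)/132).
- ICC 0.2: √(4/132) = 0.174, and × 1.96 = 0.341.
- ICC 0.4: √(6/132) = 0.213, and × 1.96 = 0.418.

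**Step 2: resulting shift in the arrest difference.** Shift ≈ 1.96 × SD × ln(odds ratio) × p(1 − p), with p(1 − p) = 0.0384, 0.1056 and 0.16 at 96%, 88% and 80%. For example, at 88%, 3-fold and ICC 0.4: 0.418 × 1.099 × 0.1056 = 4.8 points. Results in percentage points, ICC 0.2 to 0.4:

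| Arrest rate | 1.5-fold | 2-fold | 3-fold |
|---|---|---|---|
| 96% | 0.5–0.6 | 0.9–1.1 | 1.4–1.8 |
| 88% | 1.5–1.8 | 2.5–3.1 | 4.0–4.8 |
| 80% | 2.2–2.7 | 3.8–4.6 | 6.0–7.3 |

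With three arms, the 95% bound on the largest pairwise imbalance is about 1.2 times larger (3.31/2.77).

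**Step 3: what adjustment recovers.** Two-arm trials were simulated under the same assumptions, with a child random effect of SD 0.8 on the logit scale. The variance of the size-standardised difference was compared with that of the raw difference. The reduction was about 0 to 10% at 96% arrest, 1 to 18% at 88% and 2 to 24% at 80%. The upper ends need the 3-fold relation. In interval width they are about 5% (1 − √0.90), 9% (1 − √0.82) and 13% (1 − √0.76). The mean raw difference was zero within simulation error.

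**Cross-check with a binary severity marker.** Take half of lesions as more severe, 88% arrest, ICC 0.3 and a 16-point gap in arrest between milder and more severe lesions. The SD of the imbalance is √(2 × 0.25 × 2.5/132) = 9.73 points, so 95% of imbalances lie within ±19.1. The shift is 19.1 × 0.16 = 3.1 points. Over gaps of 5 to 16 points and ICC 0 to 0.5, the shift runs from 0.6 to 3.6 points. Adjustment lowers the SD of the difference from 4.17 to 3.92 (about 6%) with the 16-point gap, and from 3.99 to 3.98 with a 5-point gap.

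**Clustering, which is separate.** In three-arm null simulations of the lesion-level chi-squared test, clustered severity alone (ICC 0.3 to 0.5, 16-point gap) gave a type I error of about 7 to 8%. Adding other within-child correlation of arrest (latent 0.2 to 0.4, with severity ICC 0.3) gave about 13 to 21%.

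**The case against.** The strongest reply is that an unadjusted comparison of randomised groups is legitimate. Chance imbalance averages to zero, and an interval that allows for clustering already covers it. That stands. A reader might infer from the small arms that the regimen difference will be biased, but neither the documents nor the simulations support this. The issue is efficiency.

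Second, the gain may be negligible. The team's own pilot arrest rate is 96%. There, even a 3-fold fall in odds per SD gives shifts below 2 points, against the 16-point range (80% to 96%) that the sample-size section treats as similarly beneficial. This also stands, and it keeps the point modest.

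Third, a reader might add baseline hardness to the lost information. The Inclusion Criteria admit only teeth whose cavities are soft at entry, so hardness has little room to differ between arms. Size and location are less restricted.

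Fourth, the 13 to 21% type I error might be read as the price of omitting covariates. It comes mostly from treating lesions as independent, and it should be counted only there.

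Finally, the trial calls itself a pilot, and few failures limit modelling. At 96% arrest about 16 of 396 lesions fail (396 × 0.04), or about five per arm, and some arms may have none. This argues for one covariate and a planned answer to sparse data. It does not argue for keeping a test that ignores both the covariate and the randomised unit.

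**Conclusion.** The point holds as one of precision. The only planned between-regimen test of the primary outcome leaves out baseline size and location and does not respect the child as the randomised unit. Under the stated assumptions, a 95%-extreme size imbalance moves a pairwise difference by about 0.5 to 1.8 points at 96% arrest, 1.5 to 4.8 at 88% and 2.2 to 7.3 at 80%. Adjustment trims the variance by about 0 to 10%, 1 to 18% and 2 to 24%.

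The 88% rate, the correlations and the link between size and arrest are all assumptions. If size predicts arrest weakly, or arrest is near 96%, adjustment gains almost nothing. No figure was derived for location. The change is worth making because the data are already planned and the test needs replacing for clustering in any case.

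**What to change.** In Data Analysis, replace the chi-squared comparison with a logistic model that accounts for clustering by child: GEE with a small-sample correction, or a mixed model. Specify the following:

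- **Terms:** regimen and one pre-named covariate, baseline lesion size in mm. If the tooth is the unit, as the arrest-rate definition implies, use the largest treated lesion on that tooth.
- **Second covariate:** add anterior/posterior location only if the pooled count of non-arrested teeth, taken blind to regimen, reaches a threshold fixed in advance, for example 40. If all 396 lesions count separately, expected failures are about 16, 48 and 79 at 96%, 88% and 80% arrest. Counts by tooth may be lower.
- **Sparse data:** a penalised fit if an arm has no failures.
- **Reporting:** standardised arrest-rate differences with 95% CI, beside the raw rates.
- **Measurement:** the Baseline visit paragraph describes allocation before the lesion examination, so state that size is measured before allocation is known to the examiner.

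The cost is SAP wording, a slightly more complex model and a short procedural note on blinding. No new data item is needed. The downside is little return if arrest is near 96%.

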Third visit: Depending on the regimen children will return 4 months (Regimen 1), 6 months (Regimen 2), or 1 month (Regimen 3) later for their final follow-up visit. Parents/caregivers will complete a follow-up questionnaire administered by interviewer. Caries lesions that were treated with applications of SDF will be assessed to see if caries is arrested. Caries lesions will be assessed for colour change, size, and clinical hardness. We will also record dmft, dmfs, and PUFA scores. Clinical data will be recorded on the Clinical Record Form.

Clinical data from baseline and each follow-up visit will be linked with questionnaire data. Data will be entered into a REDCap database and saved on the secure server at CHRIM.

Oral Microbiome Sub-Study: SDF may inactivate cariogenic bacteria in vitro. There was only one study that conducted RNA analysis of plaque in six children before and after treatment (3 receiving SDF and 3 placebo) reporting no changes in relative abundance of cariogenic bacteria. In that study, not only was sample size a major limitation, but the lead author is a director of Advantage Arrest™. Our proposal to assess 30 children would provide statistical power and help elucidate if SDF leads to changes in the oral bacteriome and mycobiome. This will provide novel insights into SDF's mechanism of action, whether antimicrobial, remineralization, or both. Ten children from each regimen will have plaque samples collected. Samples will be obtained at baseline (prior to SDF application), at the first follow-up visit (prior to SDF application), and at the final visit. Nucleic acid isolation from plaque samples will be done using the DNeasy

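### The fallback for non-normal baseline-to-follow-up questionnaire data is the Mann-Whitney test, which treats paired data as independent samples

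*Combined protocol and SAP*

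**What the plan says.** All of the analysis rules are in the Data Analysis section of the combined protocol and SAP. For normally distributed interval items it names a paired t-test, to compare data "from the baseline questionnaire with that from the follow-up questionnaire within regimens (Mann-Whitney test if not normally distributed"). The bracketed test therefore replaces the paired t-test for the same comparison: baseline against follow-up, inside one regimen.

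The Implementation section shows who supplies the data. At the baseline visit, "Parents/caregivers will complete the baseline questionnaire administered by interviewer". At the third visit, "Parents/caregivers will complete a follow-up questionnaire administered by interviewer". It also states that "Clinical data from baseline and each follow-up visit will be linked with questionnaire data", so each family's two questionnaires can be matched.

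For yes/no items in this same comparison the plan chooses McNemar's test, a paired method, "to compare dichotomous data from the baseline questionnaire with that from the follow-up questionnaire within each regimen". On the significance level it says only: "A p value ≤ 0.05 will be significant". No paired rank test is named anywhere in the document.

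**The concern.** The Mann-Whitney test is built for two unrelated groups. It pools and ranks all values and computes its null variance as if each baseline value were independent of each follow-up value. Here every follow-up value belongs to a child who also has a baseline value. The plan respects the pairing for normal interval data and for dichotomous data, then drops it for non-normal interval data.

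If a child's two values are positively correlated, as repeated measurements usually are, the test's assumed variance is too large. It then rejects too rarely under the null and misses real change. The groups are small, and items on diet, hygiene or symptoms may well be skewed, so the fallback could be used. A non-significant result from it could be read as no change, in a pilot that is meant to inform a larger trial.

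**Working it through.** **Inputs from the document.** The Sample and Justification of Sample Size section gives 22 children per regimen, a loss of up to 20%, and recruitment of 28 per regimen. The significance level is 0.05; sidedness is not stated, so two-sided is assumed.

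**Reproducing the plan's figure.** 22 / (1 − 0.20) = 27.5, which rounds up to 28. This agrees. The within-regimen comparison therefore rests on about 22 pairs, and at most 28. No stated figure in the plan depends on the Mann-Whitney test.

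**Assumptions.** The document gives neither the within-child correlation nor an expected change. Skewed data were taken as log-normal, with correlation ρ on the log scale varied over a range and a shift of 0.5 SD on the log scale.

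**Why the null variance is wrong.** With equal baseline and follow-up distributions, the Mann-Whitney statistic behaves approximately like a difference in mean ranks.

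- The test assumes a variance proportional to 2/n.
- With pairs, the true variance is proportional to 2(1 − ρₛ)/n, where ρₛ is the rank correlation. For this model ρₛ = (6/π)·arcsin(ρ/2).
- A nominal critical value of 1.96 therefore acts as 1.96/√(1 − ρₛ).

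| ρ | ρₛ | √(1 − ρₛ) | Effective critical value | Approximate true type I error |
|---|---|---|---|---|
| −0.3 | −0.288 | 1.135 | 1.73 | 8.4% |
| 0 | 0 | 1 | 1.96 | 5.0% |
| 0.3 | 0.288 | 0.844 | 2.32 | 2.0% |
| 0.5 | 0.483 | 0.719 | 2.72 | 0.6% |
| 0.7 | 0.683 | 0.563 | 3.48 | 0.05% |

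**Simulation.** There were 4,000 datasets per setting, tested two-sided at 0.05. Results for 22 pairs (MW = Mann-Whitney, WSR = Wilcoxon signed-rank):

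| ρ | Type I error, MW | Type I error, WSR | Power, MW | Power, WSR |
|---|---|---|---|---|
| −0.3 | 8.2% | 4.8% | 36% | 24% |
| 0 | 4.4% | 4.4% | 34% | 30% |
| 0.3 | 2.0% | 4.6% | 33% | 40% |
| 0.5 | 0.7% | 4.4% | 30% | 51% |
| 0.7 | 0.1% | 4.7% | 28% | 72% |

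The simulated Mann-Whitney error rates follow the approximation closely. The power loss at positive correlation runs from 40 − 33 = 7 points at 0.3 to 72 − 28 = 44 points at 0.7.

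With 28 pairs (no losses), power at correlations 0.3 / 0.5 / 0.7 is 41% / 40% / 40% for Mann-Whitney and 49% / 63% / 83% for the signed-rank test. Full retention does not remove the gap.

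A separate run of 6,000 datasets with 22 pairs agrees within simulation error. At 0.5, type I error is 0.9% against 4.2% and power 31% against 51%. At 0.7, the figures are 0.1% against 4.6% and 28% against 72%.

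**The case against.** The strongest reply concerns reach. The rule covers only interval items from the questionnaires, and only when they are non-normal. Arrest rates go to chi-squared and McNemar's tests. ECOHIS and other continuous measures over time go to repeated-measures analysis of variance. The document lists no specific interval questionnaire item and gives no distribution for any, so how often the fallback would be used is unknown. This stands: the error cannot change the arrest-rate or ECOHIS conclusions, and it is a modest matter in a trial that calls itself a pilot.

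The second reply is that the size of the loss comes from assumptions. That also stands. The loss is nil at zero correlation and small at 0.3. Coarse, tied data narrow the gap: with an assumed five-category scale and correlation 0.7, power was 21% against 52%, a gap of 31 points, compared with 28% against 70% (42 points) for log-normal data in the same set of runs of 2,500 datasets.

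The third reply is that a conservative test makes no false claims. This holds for positive correlation, where the harm is missed change, but not in general: at −0.3 the error rate exceeded 8%.

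None of these replies makes the Mann-Whitney test suitable for paired data. The sentence confines the comparison to within regimens, so it cannot be read as a between-group test. The paired methods named alongside it suggest that the wrong test was named by mistake, which is a reason to correct it.

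**Conclusion.** The concern holds. The named fallback assumes independent samples and is applied to two measurements on the same children, contrary to the pairing that the plan itself uses for normal and dichotomous items. The wrong null variance follows from the design whenever the two measurements are correlated; its numerical effect rests on the assumed correlation, shift and log-normal shape. Over correlations of 0.3 to 0.7 with 22 pairs, the nominal 5% level becomes 2.0% to 0.1%, and about 7 to 44 points of power are lost. The plan should be corrected on this point, but the consequence is limited to non-normal interval questionnaire items.

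**What to change.** In the Data Analysis section, replace the bracketed Mann-Whitney fallback with the Wilcoxon signed-rank test, to be used when the within-child differences depart from normality. Apply the normality check to those differences, since they are what the paired t-test relies on; raw values can be skewed while their differences are close to symmetric. If an independent-samples rank test is wanted for comparing regimens with each other (Mann-Whitney for two groups, Kruskal-Wallis for three), state it separately; the plan names none for that purpose at present.

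The cost is an edit to one sentence. It needs no new data, visits or participants, because the questionnaires are already to be linked by child.
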